7.3 Secondary outcome statistics

To evaluate the effect of the different dressing regimes on lower limb ulcer healing, data from the two treatment arms will be compared.

Ulcer healing and more general health measures is assessed by the following parameters:

Ulcer status (healed vs non-healed)

Confidential – This document and the information contained herein may not be reproduced, used or disclosed without written permission from North Cumbria Integrated Care NHS Foundation Trust Page | 15

- Ulcer size (cm², measured with wound measuring App)
- PUSH score
- VEINES-Sym (scores for individual questions, 9 questions)
- EQ-5D-5L

To assess the Ulcer size, which are measured every 4 weeks, per treatment arm the average difference between time points will be calculated per treatment group (Wilcoxon test). To compare between the groups, Mann-Whitney U-test will be applied.

To measure patient-reported outcome measures on VEINES-Sym at baseline, week4, week 8 and week 12 (and EQ-5D-5L for week 0 and week 12); the Wilcoxon test will be applied within treatment arms (over time) whereas the Mann-Whitney U-test will be performed between treatment arms. Data of the two treatment arms will be compared by applying the Mann-Whitney U-test.

Subject to sufficient data being available, Cox proportional hazards regression analysis will be conducted to investigate the role of the dressing itself and other covariates in ulcer healing rates. Other covariates include: ulcer size and chronicity at baseline, patient age, ulcer aetiology, absence/presence of co-morbidities, ulcer location, history of recurrent ulcers.

The following descriptive statistics will be reported on where possible:

- Number of patients screened
- Number of patients eligible/ineligible, and percentage of patients consented into the trial
- Number of patients completed the trial/discontinued (plus reasons if discontinued)

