Prospective, randomised controlled trial assessing MedCu copper dressing for lower limb ulcer management

(CUPRA trial, Copper dressings for Ulcers; Prospective Randomised Appraisal)

Version 1.0, dd 18 October 2024

Chief Investigator's Statement of Ownership and Content.

I, [name], confirm that this protocol is my work and is owned by me. The protocol conforms with standards outlined in the Declaration of Helsinki 1964.

Name (PRINT):____[name]______

Signature:_______

Date: _________

RESEARCH PROTOCOL SUMMARY

| TITLE: | Prospective, randomised controlled trial assessing MedCu copper dressing for lower limb management | | | |
|----------------------|---|--|--|--|
| | (CUPRA trial, Copper dressings for lower limb Ulcers; Prospective Randomised Appraisal) | | | |
| Short title: | CUPRA trial | | | |
| IRAS ethics number | 350241 | | | |
| ISRCTN trial number | To be confirmed | | | |
| Device description | CE-marked wound dressing: MedCu (by MedCu Technologies) dressings are impregnated with copper oxide microparticles. MedCu dressings are single-use wound dressing with an internal absorbent layer and one or two external non-woven, non-adherent layers. | | | |
| Study design | Prospective, randomised controlled trial | | | |
| Primary objective | To determine the relative efficacy and safety of MedCu copper-impregnated dressing versus standard of care for the management of lower limb ulcers, measured through wound status (healed vs non-healed) at 12 weeks post-baseline. | | | |
| Secondary objectives | To determine the wider efficacy and safety of MedCu copper- impregnated dressing for the management of lower limb ulcers at 4, 8 and 12 weeks post-baseline - Any adverse events related to the use of allocated dressings, and rates of (patient-requested) discontinuation of dressing Wound status (healed vs non-healed) - Quality of Life (EQ-5D-5L) - Lower limb symptoms (VEINES Sym) - Types of dressings applied in standard care arm | | | |
| Patient population | First known randomised controlled trial of MedCu dressing. Therefore pragmatic approach to allow inclusion of wider cohort of patients. Patients with lower limb ulcer of any underlying aetiology are considered for inclusion. Index wound size should be minimum of 1cm² and can be maximum of 30cm² (only one index wound per patient to be included in study). Stratification for wound size at randomisation stage. | | | |

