3.2 Secondary objective

To determine the efficacy and safety of MedCu copper oxide impregnated wound dressing for the management of lower limb ulcers at 4, 8 and 12 weeks post-baseline

- Wound status (healed vs non-healed at 4 and 8 weeks)
- Healing rate (ulcer size, PUSH score)
- Generic quality of Life (EQ-5D-5L)
- Lower limb symptoms (VEINES Sym)

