5.1.1 Randomisation and Blinding aspects

Following written consent patients will be allocated at random to the one of two treatment arms. Participants are stratified by ulcer size (PUSH score) at baseline, ie week 0.

A non-restricted randomised sequence will generated for each of the two groups using a freeware randomisation programme, see https://www.sealedenvelope.com/. The randomisation will be stratified by ulcer size, with one group being those with a PUSH score of up to and including 8, or a PUSH score of 9 or higher

Each next randomisation allocation will be obtained from the sealedenvelope.com account for this CUPRA trial.

As the study involves different looking dressings, it is not possible to achieve blinding for the participants. However, statistical analysis is carried out blinded to group allocation, by persons who have not had contact with study participants.

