5.2 Eligibility criteria

5.2.1 Inclusion criteria

- Aged 18 years or over
- Women to be of non-childbearing potential (ie post-menopausal)
- Lower limb ulcer sized between 1 to 30 cm²
- Patients can be newly presenting to or existing users of the specialist service in question
- Patients with recurrent wounds, including multiple wounds, are eligible; largest eligible (ie <30cm²) ulcer to be index wound
- If infection occurs and systemic antibiotics applied, whilst in study, then this is not deemed an exclusion criterion.
- Chronicity: clinical diagnosis of ulcer with wound duration > 30 days and < 1 year from patient becoming aware.
- Prophylactic systemic antibiotic use is not an exclusion criterion
- Mental and physical ability to give consent and complete study activities
- Underlying pathology of lower limb ulcer can be venous, mixed venous-arteria, arterial, or through different underlying aetiology. Recognised co-morbidities that may contribute to the development of lower limb ulcers (e.g. diabetes, rheumatoid arthritis, peripheral vascular disease) are not an exclusion criterion.
- For leg ulcers: Patient is suitable for, and willing to wear, compression therapy, or valid clinical reason why they should not be prescribed compression therapy.

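### The secondary ulcer-size outcome is a plain cm² difference across entry sizes of 1 to 30 cm², so a healed small ulcer can score below a large ulcer that barely shrinks

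*Protocol*

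**What the plan says.** Section 3.2 of the protocol lists "Healing rate (ulcer size, PUSH score") among the secondary objectives. Section 7.3 gives the measure as "Ulcer size (cm², measured with wound measuring App") and sets its derivation: "per treatment arm the average difference between time points will be calculated per treatment group (Wilcoxon test"). The between-arm analysis follows in one sentence: "To compare between the groups, Mann-Whitney U-test will be applied". That sentence does not say whether the test ranks the change or the area at each visit. No percentage change, log ratio or baseline adjustment is given for this outcome.

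Eligibility allows a wide range of sizes. Section 5.2.1 has "Lower limb ulcer sized between 1 to 30 cm²", and the protocol summary agrees: "Index wound size should be minimum of 1cm² and can be maximum of 30cm²".

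Three other features bear on the point:
- Healing is also recorded separately as "Ulcer status (healed vs non-healed"), which is the primary outcome at week 12.
- Section 5.1.1 uses two size strata: "The randomisation will be stratified by ulcer size, with one group being those with a PUSH score of up to and including 8", and the other from 9 upwards.
- Baseline ulcer size is a covariate only in the Cox model of section 7.3, which is run if there are enough data.

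**The concern.** The largest reduction that an ulcer can show in cm² is its own entry area. With a 30-fold range of entry areas, a cm² reduction therefore reflects how large the ulcer was as well as how well it healed. Among ulcers that heal completely, the score is exactly the starting area. An outcome meant to express healing rate can then place complete healing below slight shrinkage.

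At stake is a named secondary efficacy outcome. It could appear to disagree with the primary result. Variation in starting size also adds noise that makes a true dressing effect harder to see in a trial of 33 per arm.

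**Working it through.** **Plan's own figure.** The protocol gives no power or expected value for ulcer size. Table 4 only fixes the group sizes used here. With effect size 0.40, (1.960 + 0.842)² / 0.40² = 49.1, so 50 in total (25 per arm). Adding 30% gives 50 × 1.3 = 65, made even as 66 (33 per arm). Both figures reproduce.

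**Arithmetic from the entry limits alone.**
- A 1 cm² ulcer that heals loses 1 cm². A 30 cm² ulcer beats it once it shrinks by more than 1/30 = 3.3%. For example, 30 to 28.9 cm² is a loss of 1.1 cm², or 3.7%.
- A 5 cm² ulcer that heals loses 5 cm². A 30 cm² ulcer going to 24.9 cm² loses 5.1 cm², or 17%, and beats it.

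Three illustrative records:

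| Record | Area, cm² | cm² change | Reduction |
|---|---|---|---|
| A, healed | 1 to 0 | -1 | 100% |
| B, not healed | 30 to 27 | -3 | 10% |
| C, not healed | 20 to 12 | -8 | 40% |

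On cm² change the only healed ulcer ranks last. On percentage change it ranks first.

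**Simulation.** From Table 4: 40% against 60% healed, with 25 or 33 per arm. Everything else is assumed, because the protocol gives no size distribution or expected shrinkage:
- entry area uniform, log-uniform or truncated log-normal (median parameter 5 cm²) on 1-30 cm²;
- unhealed ulcers at a median of 60% of baseline area (log-SD 0.5) or 80% (log-SD 0.4), the same in both arms;
- healing independent of size, or less likely in larger ulcers (log-odds falling by 0.7 per unit of log area).

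This makes 3 × 2 × 2 = 12 scenarios, with 1,000 trials per power estimate (Monte Carlo error about 1-1.5 points). With uniform sizes and size-dependent healing, overall healing falls to 36%. In the other scenarios it stays at 49-50%.

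*Reversed pairs.* On cm² change, a healed ulcer scored worse than a randomly chosen unhealed one in 10-36% of pairs. On percentage change the share is 0 by construction.

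*Influence of starting size.* The rank correlation of cm² change with starting area was 0.30 to 0.72, and with relative healing 0.42 to 0.81. Starting size was the stronger of the two in 4 of 12 scenarios.

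*Mann-Whitney power, range over the 12 scenarios:*

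| Variable ranked | 25 per arm | 33 per arm |
|---|---|---|
| cm² change | 8-16% | 10-20% |
| Percentage change | 18-27% | 23-35% |
| Area at week 12 | 16-26% | 19-35% |

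Percentage change had the higher power in every scenario. The gap was smaller when healing depended on size. With uniform sizes, 60% median remaining and 33 per arm, it was 15% against 35% when healing was independent of size, and 13% against 23% when it was not.

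*Other assumed distributions.* Further runs at 25-33 per arm gave 16-40% reversed pairs. Power was 9-20% (cm²) against 14-34% (proportion remaining) when only healing differed. It was 24-45% against 34-60% when unhealed ulcers also shrank more in one arm. In a separate null check with other assumed inputs, the error rate was about 5% on both scales.

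**The case against.** **The primary outcome is untouched.** Healed status is analysed on its own, and no healed patient is misclassified. This stands. A reader might infer that healing as a whole is mis-scored, but the fault is confined to the secondary size measure.

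**Dominance of starting size is not shown.** A reader might conclude that the arm comparison mainly ranks starting area. The protocol gives nothing to establish this, and in the assumed scenarios starting size was usually not the stronger driver. Heavy influence is as far as the evidence goes.

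**There is no systematic bias.** Randomisation, with two PUSH strata, balances starting size in expectation, and the null error rate is held. This stands. What remains is noise, chance imbalance in small arms and a scale that is hard to interpret.

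**The ranked variable is not named.** If the Mann-Whitney test ranks area at each visit, a healed ulcer at 0 cm² ranks best and the reversal disappears between arms. This is a fair reading. However, the difference is the only derived size quantity in the text, and the within-arm analysis uses it in any case. Leaving absolute or relative change to an analysis plan would be ordinary, but here the protocol states a difference of a measure in cm².

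**Baseline adjustment also works.** It may be tempting to say that adjusting a cm² difference leaves it mis-ordered, but the three records show otherwise. If the expected loss is an assumed 40% of baseline, observed minus expected change is A: -1 + 0.4 = -0.6; B: -3 + 12 = +9; C: -8 + 8 = 0. The healed ulcer now ranks best. A ranks ahead of C whenever -1 + s < -8 + 20s, that is, for a proportional loss s above 7/19 = 37%. Percentage change is therefore not the only repair.

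**Power stays low on either scale.** This is true. At 40% against 60%, even the healed/non-healed comparison has only about 29% power at 25 per arm and 37% at 33. On the relative scale all healed ulcers tie, so when only healing differs the test largely repeats that comparison. This limits the gain but does not justify a scale that loses more.

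**Conclusion.** The concern holds for the secondary ulcer-size outcome. The reversal follows from the protocol's own entry limits and needs no assumption, provided that the cm² difference is what is ranked.

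Its size rests on assumed distributions. Roughly 10-40% of healed/unhealed pairs are reversed. Power at 25-33 per arm is about 8-20% on cm² change against 14-35% on the proportion of baseline area remaining when only healing differs. The advantage is smaller when healing depends strongly on size.

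The two PUSH strata do not rescale the score, and the conditional Cox model analyses a different endpoint, so neither removes the problem. The harm is lost power and a misleading scale. The documents do not support a claim of bias or of any effect on the primary analysis. The change is worth making because it uses the same measurements.

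**What to change.** In section 7.3, define the ulcer-size outcome as percentage change in area from week 0, with a healed ulcer counted as a 100% reduction, at weeks 4, 8 and 12. The proportion of baseline area remaining is equivalent. State that this is the variable that the Mann-Whitney test compares between arms, and report cm² change descriptively. Alternatively, keep an area measure and adjust the between-arm comparison for baseline area, again naming the variable analysed.

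The cost is an amendment to one or two sentences. The existing app measurements suffice, with no added visits or patients. One small drawback is that percentage change is noisier for the smallest ulcers.

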8. DATA HANDLING AND MONITORING

Data arising from this study is confidential. Identifiable information can only be accessed by delegated members of the study team. Anyone in the research team who does not have a substantive contract with North Cumbria Integrated Care NHS Foundation Trust will need to apply for a letter of access via the NIHR research passport scheme, should they require access to identifiable study data.

Patient identifiable data will only be used within each respective Trust and by the core research team. All identifiable data is stored on password protected NHS computer systems. Anonymised data will be shared and stored using security-enabled systems such as password-protection and encryption of e-mails and files. The requirements of the Data Protection Act, GDPR, and NHS Code of Confidentiality will be followed at all times. All researchers will be fully trained in NHS Confidentiality and GCP. Participants' GP practices will be informed that they are taking part in the study.

All paper data will be held in secure locked environments in the office of the Research & Development department in the Carlisle, Whitehaven, Workington and Wigton hospital locations. Data released (e.g. by publication) will contain no information that could lead to the identification of an individual participant. Upon completion of the study the site files will be archived for a period of 10 years in line with local archiving policy and procedures. Direct access to data only will be granted to authorised representatives from the sponsor / host institution, grant funder and medical device

Confidential – This document and the information contained herein may not be reproduced, used or disclosed without written permission from North Cumbria Integrated Care NHS Foundation Trust Page | 16

provider Creed Health, and the regulatory authorities to permit trial-related monitoring, audits and inspections.

This investigator-initiated trial will be monitored in terms of conduct of the study by the in-house research team, led by the Chief Investigator, who will convene on a monthly basis in person or via phone/e-mail. A trial steering committee will not be convened for this trial. The study can be audited by the in-house R&D department as part of their rolling audit programme of sponsored and hosted research studies. As part of the research grant agreement, anonymised study data will be shared with both MedCu company for review and for potential publication purposes. No identifiable data, including on potential exemplar case photos, will be contained in any of this data.

9. GOVERANCE OF STUDY

9.1 Approvals

This study will be conducted in compliance with the protocol approved by the Health Research Authority, National Research Ethics Service, and local Trust R&D Approval, and according to Good Clinical Practice standards including the Declaration of Helsinki (1964, Amended Oct 2013). No deviation from the protocol will be implemented without the prior review and approval of the aforementioned review bodies, except where it may be necessary to eliminate an immediate hazard to a research subject. In such case, the deviation will be reported according to policies and procedures

9.2 Sponsor & Indemnity

North Cumbria Integrated Care NHS Foundation Trust is the sponsor of this study and therefore NHS indemnity applies for design, conduct and management of the study. MedCu company has provided a grant for this study by means of provision of the dressing, worth £3,500.

Patients will not be given financial incentives for taking part in the study. Travel expenses are not offered in this study since patients are seen in clinic as part of their normal care pathway.

9.3 Medical Device management and use of different compression bandage brands

MedCu dressings will be stored in the NHS store and clinic rooms at the temperature recommended by the respective manufacturers. No requirement for involvement pharmacy or clinical trials pharmacist. Standard approved and available stocks of dressings and compression bandaging to be used for any standard care activities.

9.4 End of Study

This will be the date of the final research visit of the last participant across the whole trial.

10. PUBLICATION AND DATA-SHARING POLICY

The study will be registered on the ISRCTN website, in line with CONSORT guidelines on good practice in clinical research.

The results of this study will be disseminated through:

- Peer-reviewed manuscript in scientific journal
- Internal report

APPENDIX 1. INTERVENTION DEVIATION AND LOWER LIMB ULCER INFECTION

There may be incidences where a participant may either:

- Develop a reaction to the allocated dressing.
- Becomes completely non-compliant (possibly due to allocated dressing being uncomfortable, or eg hospital admission)
- Improve to such an extent that allocated dressing is no longer indicated.

In such instances the patient and/or clinician can opt to stop or pause treatment with the dressing in question. If this occurs, this needs to be recorded (date and reason), and the decision can then be made to either:

- Discontinuation of intended dressing due to improvement in symptoms (including wound healed). Participant will still continue to be assessed as per planned dates and timepoints.
- Change over to an alternative dressing that is not the originally allocated type. This is allowed but only if there are clinical indications to do so or at patient request if they cannot tolerate the allocated dressing. Patient can later in trial period be transferred back to original allocated bandage type if required.
- Pausing or discontinuation of wound dressing when not clinically indicated. Even if lower limb ulcer persists and patient no longer wears allocated dressing, they can still continue in the trial if they wish. Outcome measures will continue to be recorded as per planned dates and time points.
- Pause or discontinuation due to adverse event. Patient can remain in trial provided they are capable to continue with follow-up schedule and completion of outcome measures. If not possible, see next point regarding 'Withdraw patient from study'.
- Withdraw patient from study.
 - o At the request of the patient
 - For clinical reasons, eg if the leg ulcer has deteriorated to such an extent that emergency surgical or medical intervention is required which means return to use of any dressing in reasonable time frame (within time to next trial follow-up visit) is not feasible. In this case, this needs to be reported as a (Serious) Adverse Event if discontinuation is due to deterioration of the index wound or index leg only.

When overall trial participation for a patient is finished early, the participant will still be asked to complete the relevant questionnaires (provided they have capacity to do so):

- Week 4, week 8 and week 12 VEINES Sym questionnaire
- Week 12 EQ5D5L QoL questionnaire

Infection and use of antibiotics during trial

Patients do not have to withdraw from the study if clinically determined infection occurs, as long as clinically there is a reason to continue with wound dressing and it is deemed safe to do so. This applies for both oral and intravenous antibiotics use. If a treating clinician determines that the allocated dressing should stop then this will be classed as an intervention deviation – see above.

APPENDIX 2 – CUMBRIA WOUND FORMULARY (2024) Please see https://medicines.necsu.nhs.uk/cumbria-wound-formulary/

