6. SAFETY

6.1 Potential risks & benefits to study participants

There is no anticipated personal safety risk associated with taking part in this study. If the research team learns of important new information that might affect patient's desire to remain in the study, he or she will be told. Appropriate precautions are in place to ensure medical and personal information is kept safe through adhering to appropriate governance regulations. Participants in both the treatment arms will be allocated a wound dressing that is used for its intended licensed purpose and that is available via standard care routes. Any adverse events will be recorded, as outlined in sections below.

Apart from being allocated to a different type of wound dressing, all patients will receive the indicated clinical care they would receive when not in the trial. They will otherwise be cared for in exactly the same manner as they normally would. Participants cannot claim payments, reimbursement of expenses or any other benefits or incentives for taking part in this research.

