7.2 Primary outcome statistics

The primary objective for this pilot study wound healed status at week 12.

For comparative performance (superiority) analysis, any statistically significant difference (p-value < 0.05) between the two treatment arms will be determined with Chi-squared test.

Analyses will be performed on a per protocol basis, with only those participants that data is available for included in the analysis. Data will first be collated in Microsoft Excel, followed by analyses performed using SPSS v20.

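### Section 7.2 labels the primary superiority analysis per-protocol but defines it by data availability, so patients who leave their allocated dressing are kept on one reading and dropped on the other

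*Protocol*

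**What the plan says.** **Changing or stopping the dressing (Appendix 1).** One listed option is "Change over to an alternative dressing that is not the originally allocated type". It is conditional: "only if there are clinical indications to do so or at patient request if they cannot tolerate the allocated dressing". A later return to the allocated type is allowed. The appendix also covers pausing or stopping, and the situations it lists are a reaction, complete non-compliance and improvement. If a wound infection occurs: "If a treating clinician determines that the allocated dressing should stop then this will be classed as an intervention deviation". No consequence for the analysis is attached to that classification.

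**Follow-up after leaving the dressing (Appendix 1).** Under the option to pause or stop while the ulcer persists, the patient may remain in the trial: "Outcome measures will continue to be recorded as per planned dates and time points". Patients who stop because of improvement are still assessed as planned. Those who stop for an adverse event may stay if they can complete the visits. The change-over option implies the same, since it provides for a return to the allocated type.

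**The analysis set (section 7.2).** The primary test is a chi-squared comparison for superiority on healed status at week 12. The rule for who enters it is: "Analyses will be performed on a per protocol basis, with only those participants that data is available for included in the analysis". Section 5.3 adds that data gathered before a withdrawal are used. No other section states an analysis set.

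**The concern.** The two halves of the 7.2 sentence select different patients. In ordinary usage a per-protocol set leaves out people who departed from the assigned treatment. A set defined by available data leaves out only people with no outcome. Appendix 1 creates a group for whom this matters: off the allocated dressing, still in the trial, with a week-12 result.

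For a superiority claim the choice is not cosmetic. Leaving an allocated dressing happens after randomisation and is tied to how the wound and the patient are doing. Section 5.1.1 says participants cannot be blinded, so the decision is made knowing the arm. Dropping those patients compares selected remnants of the two arms. If the rule stays open, it could also be settled once it is known which patients switched and whether they healed. The blinded analysis promised in 5.1.1 does not supply the missing rule.

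**Working it through.** **1. The two readings, case by case.**

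| Patient with a week-12 outcome | Description in 7.2 (data available) | Label in 7.2 (per-protocol) |
|---|---|---|
| Stayed on allocated dressing | kept | kept |
| Changed to another type | kept, arm not stated | normally excluded |
| Stopped, ulcer persisting | kept | normally excluded |
| Clinician-ordered stop in infection, classed as a deviation | kept | normally excluded |
| Stopped because of improvement | kept | unclear |

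The readings agree only on the first row. Patients with no week-12 outcome are out of the set either way.

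**2. The plan's own figure.** Table 4 in section 5.1 gives 50 patients before attrition and 66 after. With effect size w = 0.40, two-sided 5% and a 1-df chi-squared test, N = 50 gives power 0.807. Then 50 × 1.30 = 65, rounded to 66 for equal arms. So there are 33 randomised per arm, and 25 per arm is the evaluable number the plan aims for. This point uses only those two counts and the rates of 40% and 60%.

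**3. What exclusion can do (illustration, counts assumed).** Suppose there is no true effect, healing is 40% in both arms and 25 per arm are evaluable, so 10 of 25 heal in each. Remove deviators from one arm only:
- 3 not healed: 10/22 = 45%; 5 not healed: 10/20 = 50%.
- 3 healed: 7/22 = 32%; 5 healed: 5/20 = 25%.

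The other arm stays at 40%. With no treatment effect the apparent difference runs from +10 to −15 points, depending only on who is removed. Both kinds of removal are conceivable, because Appendix 1 lists reactions and non-compliance as well as improvement.

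**4. What keeping switchers can do (illustration, c assumed).** Let a share c of controls move to MedCu and take its 60% rate, with everyone counted as randomised. The control rate is 40 + 20c and the difference is 20(1 − c) points.
- c = 10%: 42% against 60%, 18 points.
- c = 20%: 44% against 60%, 16 points.
- c = 30%: 46% against 60%, 14 points.

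The two-proportion normal formula (two-sided 5%, 80% power) gives n per arm of 96.92 with no switching and 119.89, 151.87 and 198.32 for the three cases. The ratios are 1.24, 1.57 and 2.05, close to 1/(1 − c)² = 1.23, 1.56 and 2.04. They are used only as ratios. The formula's 96.92 per arm does not match the plan's 25, which is a separate question about the effect size that was entered.

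**5. Why step 4 gives no bounds.**
- One crossing control costs 20/33 = 0.6 points if all 33 are evaluable, but 20/25 = 0.8 points if 25 are.
- Patients who switch are selected and could gain more, or less, than the average 20 points.
- MedCu patients may also switch. With 10% each way the rates are 42% and 58%, a difference of 16 points instead of 18.

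**The case against.** **7.2 has a workable reading.** The only operational rule in the sentence is availability of data. Section 5.3 retains what was collected before withdrawal, Appendix 1 retains patients who leave the dressing, and no sentence removes a switcher. On this view 7.2 is an available-case analysis with the wrong label, and the handling of deviations can wait for a statistical analysis plan. Much of this stands, and it may well be what was meant. But the label then has no content, and the arm in which a switcher counts is still unstated. The protocol also did not leave the set open: it fixed it in conflicting terms, so a later plan would have to overrule half of the sentence.

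**Control-to-MedCu crossover.** A reader might infer that the protocol wrongly lets controls receive the test product. It is true that Appendix 1 names no excluded destination. Section 6.1 says both arms get "a wound dressing that is used for its intended licensed purpose and that is available via standard care routes", and section 9.3 says "MedCu dressings will be stored in the NHS store and clinic rooms". But the inference rests on silence. Change-over needs a clinical indication or intolerance, and slow healing is not a listed situation. Controls have a range of alternatives, antimicrobial types included (4.5.2). Section 9.3 directs: "Standard approved and available stocks of dressings and compression bandaging to be used for any standard care activities". Section 9.2 describes MedCu as supplied through a grant in kind for this study. Appendix 2 is only a link, so whether the formulary lists MedCu cannot be checked. In a trial described as pragmatic, withholding a CE-marked dressing for 12 weeks despite a clinical indication is a trade-off. The objection succeeds on this part.

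**Conclusion.** The point holds for the analysis set. Section 7.2 gives two incompatible rules for patients in either arm who leave the allocated dressing and have a week-12 outcome, and Appendix 1 makes such patients possible. This follows from the text and needs no assumption beyond the usual meaning of per-protocol. It should be corrected before the analysis.

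Its practical size is unknown, because the protocol gives no switching rate. Two stronger readings are not supported:

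- *That exclusion would favour MedCu.* The direction depends on who deviates in each arm, and the counts in step 3 of the working are invented to show both signs.
- *That 18, 16 and 14 points are floors on the difference, or that the sample-size ratios are a ceiling on the harm.* They rest on assumed shares, an average effect in switchers and one-way switching.

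**What to change.** In section 7.2 replace the per-protocol wording with: *all randomised participants with week-12 outcome data are analysed in their randomised arm, whatever dressing they received.* If a per-protocol analysis is wanted, make it a sensitivity analysis and list beforehand which Appendix 1 events remove a patient. State there how stopping because the wound has improved or healed is treated.

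Report, by arm, the share who left the allocated dressing, including controls who received MedCu. The data are already planned: dressing use status at weeks 0, 4, 8 and 12 (Table 3 in 4.3), the specific dressing used (7.1), and the date and reason for any stop (Appendix 1).

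The cost is one sentence replaced and a short definition added, with no new data collection. The drawback is dilution from switching, which the reported shares let readers judge.

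Optionally, the sponsor may decide that a control's alternative dressing should not be MedCu before week 12. That would limit dilution but remove one treatment option for those patients, and the fix to 7.2 does not depend on it.
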